## 8 Study Analysis Plan

### 8.1 Study Analysis

The results of the study: subject demographics, baseline assessments, treatment parameters, treatment evaluations and follow-up assessments will be summarized and descriptive analysis will be performed. Continuous variables will be compared between the two groups using independent samples Student's t-test or Mann-Whitney U test. A p-value < 0.05 will be considered as significant.

Adverse events reported will be listed, documenting course, outcome, severity, and possible relationship to the treatment. The modified Clavien classification will be used to evaluate severity of Adverse Events [12].

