### 5 Outcome Measures

#### 5.1 Primary Endpoints

- Procedure time
- Usage of alternative stone extracting devices
- Catheterization time
- Time to hospital discharge
- Stone clearance based on 1 month follow-up imaging data

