## 6 Patient Population

### 6.1 Source and Sample Size

Subjects shall be selected by the physician within his patient population. One (1) site will participate in this study and will treat twenty (20) subjects. Enrolled subjects that did not complete the full course of the study will be discarded from performance analysis if they have not returned for the one month follow-up visits.

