#### 6.2.1 Inclusion Criteria

6.2.1.1 Subject will be older than 18 years of age

6.2.1.2 Subject was diagnosed with renal calculi meeting the following criteria:

- Largest stone measures no more than 2cm on a single diameter and is no less than 0.8cm as defined by X-ray or CT.
- Accumulative stone burden (addition of all stone diameters) is no more than 2.5cm.

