### 7.3.3 Subject randomization

Allocation of the treatment parameters used during the procedure will be performed using study randomized envelopes. The sponsor will provide the site with sealed envelopes containing "stone breaking" or "stone dusting" treatment parameters. Randomization will be divided into two groups of patients (1-10 and 11-20) with randomization ratio of 1:1 in each group. The randomization list will take into consideration additional subjects that will be required to replace subjects that have dropped from the study. If any subject drops out from the study and is replaced by another subject randomization will continue as per the original randomization scheme (this new subject will not receive the randomization of the subject that was replaced).

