### 7.4 Pre-treatment evaluation

The following examinations are included in the standard of practice for subjects with renal calculi and may have been performed prior to the subject enrollment. Medical history as well as measurements that were completed prior to study enrollment will be used as baseline data for the study.

- A complete history and physical examination and total duration of the patient's symptoms;
- Blood and urine tests including urinalysis, urine cultures, complete blood count (CBC).
- Stones sizes and locations measured using the most recent X-ray or abdominal Computed Tomography imaging performed.

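### Procedure time is compared without adjusting for baseline stone burden, which is already measured; adjusting would probably add precision and would guard a 20-subject trial against chance imbalance

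*Combined protocol and SAP*

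**What the plan says.** Section 5.1 lists "Procedure time" first among five primary endpoints. Section 6.1 sets the size: "One (1) site will participate in this study and will treat twenty (20) subjects".

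For the analysis, section 8.1 says: "Continuous variables will be compared between the two groups using independent samples" tests, either Student's t or Mann-Whitney U. It adds: "A p-value < 0.05 will be considered as significant". Baseline assessments are to be summarized descriptively. No covariate, regression model or stratified comparison appears anywhere in the document.

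On stone size, criterion 6.2.1.2 admits a largest stone between 0.8 and 2 cm and also requires: "Accumulative stone burden (addition of all stone diameters) is no more than 2.5cm". Section 7.4 lists among the baseline data: "Stones sizes and locations measured using the most recent X-ray or abdominal Computed Tomography imaging performed".

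On allocation, section 7.3.3 says: "Randomization will be divided into two groups of patients (1-10 and 11-20) with randomization ratio of 1:1 in each group". Stone size is not a stratification factor.

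**The concern.** The eligible range is wide for the quantity that the laser has to destroy. The largest diameter can vary 2.5-fold, which is about 16-fold in volume for similarly shaped stones. Section 1.2 expects dusting to save time through quicker fragmentation, less extraction and less repositioning. It is reasonable to infer that each of these depends on how much stone is present.

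Neither the randomization nor the analysis deals with this. Variation in procedure time due to stone size goes into the error term and lowers power. If one arm of ten happens to receive larger stones, the unadjusted difference mixes that imbalance with the effect of the laser settings. The imbalance can mimic a difference or mask one. A baseline table would show the imbalance but would not correct the estimate, and a decision to adjust taken after seeing it would be open to the charge of selective analysis.

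**Working it through.** **Inputs from the document.** Total 20 subjects (6.1), 1:1 allocation (7.3.3), so 10 per arm; significance level 0.05 (8.1); largest stone 0.8 to 2 cm and summed diameters at most 2.5 cm (6.2.1.2).

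**Assumptions, because the document is silent.** Two-sided test; normally distributed outcome (after logging, if times are skewed); a true effect of 1 SD of procedure time; correlation r between burden and time within arms, varied from 0 to 0.8. The plan gives no effect size, SD or power for its 20 subjects, so there is no design figure to reproduce.

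**Eligible range.**
- Largest diameter: 2 / 0.8 = 2.5-fold; 2.5³ = 15.6-fold in volume for similar shapes.
- Summed diameter: 2.5 / 0.8 = about 3.1-fold.

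**Chance imbalance.** In SD units of burden, the difference between arm means has standard error √(2/10) = 0.447.
- P(difference > 0.25 SD) = 58%
- P(> 0.5 SD) = 26%
- P(> 0.8 SD) = 7%

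As an illustration, suppose the largest diameter were uniform on 0.8 to 2 cm. Its SD would be 1.2/√12 = 0.346 cm, and the standard error of the difference 0.346 × 0.447 = 0.155 cm. The arm means would then differ by more than 0.2 cm in 20% of trials and by more than 0.3 cm in 5%.

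**Unadjusted test.** From the noncentral t distribution with 18 df, power is 56% for a 1-SD effect. Reaching 80% needs an effect of 1.325 SD.

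**Adjusted test.** Analysis of covariance with one covariate leaves 17 df. Its expected variance relative to the unadjusted estimate is (1 − r²) × 17/16. The SD of the estimated effect is 0.447 times the square root of that ratio. Power comes from 100,000 simulated trials at each r.

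| r | Variance ratio | SD of estimate | Adjusted power, 1-SD effect | Unadjusted power |
|---|---|---|---|---|
| 0 | 1.06 | 0.46 | 53.5% | 56% |
| 0.3 | 0.97 | 0.44 | 57.4% | 56% |
| 0.4 | 0.89 | 0.42 | 60.9% | 56% |
| 0.5 | 0.80 | 0.40 | 66.0% | 56% |
| 0.6 | 0.68 | 0.37 | 72.6% | 56% |
| 0.7 | 0.54 | 0.33 | 81.5% | 56% |
| 0.8 | 0.38 | 0.28 | 92.5% | 56% |

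Break-even is where (1 − r²) × 17/16 = 1, so r = √(1/17) = 0.24. At the 1.325-SD effect that gives the t-test 80% power, adjustment gives 88% at r = 0.5 and 97% at r = 0.7.

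**Error rates.** Over all randomizations both tests hold about 5% type I error. Among trials where mean burden differs by more than 0.5 SD, the unadjusted test's type I error is 6.6% at r = 0.3, 9.5% at r = 0.5 and 13.7% at r = 0.7. The adjusted test stays at about 5%.

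**The case against.** The sponsor could fairly answer as follows.

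- **The planned test is valid.** Chance imbalance is part of the null distribution under randomization. This is correct, and no inflation of the overall error rate is claimed. What remains is lost precision, and bias conditional on the allocation obtained. At r = 0.5, an imbalance of 0.5 SD shifts the unadjusted estimate by 0.25 SD, against a standard error of 0.447 SD.
- **The gain depends on an unknown r.** This stands. Below about 0.24 adjustment costs a little, at 0.3 the gain is about one point of power, and it becomes material only from about 0.5.
- **Procedure time may include steps unrelated to stone size.** Its start and stop points are not defined. If it covers guidewire placement, dilation, ureteral inspection and stenting (7.5.3 to 7.6.4), r would be diluted.
- **The range is a limit, not a distribution.** This stands. The actual spread of stone sizes among enrolled subjects may be narrower than eligibility allows.
- **Summed diameter is an imperfect measure.** One 2 cm stone and two 1 cm stones have the same sum, but for similar shapes their volumes are in the ratio 8 to 2. Section 7.4 also allows sizing by X-ray or CT while 7.2.1.3 specifies CT; mixed measurement would lower the usable r.
- **Twenty subjects are too few for modelling, and the study is largely descriptive.** This carries less weight. One covariate leaves 17 df and type I error is held. The plan sets a significance threshold, and section 4.1 aims to demonstrate efficiency.

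These points limit how large a gain to expect. They do not favour leaving the covariate out, because the worst loss is small and the plausible gain is much larger.

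**Conclusion.** The concern holds as an improvement that should be made, not as an error of validity. The plan compares a primary endpoint without using a baseline measurement it already requires, and nothing in the design balances that measurement between arms. There is about a one-in-four chance that mean burden differs by more than 0.5 SD. If r is 0.5 to 0.7, adjustment raises power for a 1-SD effect by about 10 to 25 points; if r is 0, it loses between 2 and 3 points. These figures rest on 10 evaluable subjects per arm, a two-sided test, normal data on the analysis scale, and assumed values for r and the effect size. That burden strongly influences procedure time is a reasonable inference; the document gives no estimate of it.

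**What to change.** In section 8.1, name the main comparison of procedure time as an analysis of covariance: log procedure time on randomized group plus log accumulative stone burden, with burden as defined in 6.2.1.2. Report the adjusted ratio of times with its 95% confidence interval, state that the test is two-sided, and keep the unadjusted comparison as a sensitivity analysis. Use this covariate only; with 20 subjects, more would cost too many degrees of freedom.

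Two short additions would protect the benefit. First, say which imaging reading supplies the burden value, reconciling 7.2.1.3 with 7.4. Second, define when procedure time starts and stops. All of this should be fixed before any outcome data are seen, including those for the interim look in 8.2.

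The cost is a few sentences in the plan and one degree of freedom. No extra subjects, visits or measurements are needed.

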Due to its flexibility advantage, holmium lithotripsy is mostly described as the modality of choice for retrograde ureteroscopic fragmentation of ureteral stones and small renal stones. During these procedures low power settings (low energy and frequency) are commonly used, due to the retropulsion effect of the holmium laser on the stone that prolong the lithotripsy process. These low power settings limit the fragmentation efficacy of the laser.

Several methods to overcome retropulsion have been shown in in-vitro testing, including reduced energy per pulse used at higher frequencies and longer pulse duration [8, 9, 10]. The use of high

frequency (40-80Hz) at low energy settings (0.2-0.5) has been suggested to enable fragmenting the stone into very fine particles (dust) that are washed out spontaneously. The use of decreased energy per pulse minimizes retropulsion, whereas the use of high frequency enables the application of the same accumulated energy to the stone, thus leading to similar lithotripsy. The application of these parameters in a clinical scenario has been limited, but explorative studies have shown that the use of stone dusting settings with high frequency & low energy can reduce operative time while demonstrating excellent clearance of renal stones at one month post procedure [14]

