### 8.2 Interim analysis

Interim analysis of the immediate post-operative data will be performed after at least 10 subjects underwent surgery in order to assess the immediate study results. Treatment safety and both primary and secondary endpoints will be analyzed following the completion of all study subjects follow-up period.

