## 10.9 Training Requirements

PI and all study personnel are well familiar with the procedure and device operation including all related tools and equipment. No training or additional instructions are required prior to study initiation.

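### Section 8.1 leaves out the two randomization groups of 7.3.3, so a shift in outcome between them would make the planned tests conservative and cost some power

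*Combined protocol and SAP*

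**What the plan says.** Below, *block* means one of the two sets of ten subjects and *arm* means the treatment, because the protocol uses the word group for both.

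- **Allocation (7.3.3):** "Randomization will be divided into two groups of patients (1-10 and 11-20) with randomization ratio of 1:1 in each group". A replacement subject takes the next code on the list, not the allocation of the subject replaced.
- **Size (6.1):** "One (1) site will participate in this study and will treat twenty (20) subjects". Subjects who do not return at one month are left out of the performance analysis.
- **Analysis (8.1):** "Continuous variables will be compared between the two groups using independent samples", followed by Student's "t-test or Mann-Whitney U test". "A p-value < 0.05 will be considered as significant". The two groups in that sentence are the arms. No section adds a term or stratum for block.

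Four other places bear on whether outcomes might shift between blocks.

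- **1.1**, on the dusting settings: "The application of these parameters in a clinical scenario has been limited".
- **10.9:** "No training or additional instructions are required prior to study initiation". The sentence before it gives the reason, which is that staff already know the procedure and the equipment.
- **8.2:** "Interim analysis of the immediate post-operative data will be performed after at least 10 subjects underwent surgery".
- **7.1:** enrollment is expected to take 8-10 weeks.

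**The concern.** Fixing the arm ratio within each block protects the comparison against a change over time. An analysis without block keeps that protection for the estimate but not for its standard error. Variation between blocks, which the design has already removed from the arm difference, is still counted as noise. The endpoints affected are the continuous ones: procedure time, catheterization time and time to discharge. Procedure time is the most open to change as cases accumulate. With 20 subjects and no power calculation in the plan, there is little power to spare.

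**Working it through.** **Inputs from the documents.** 20 subjects, 10 per arm; two blocks of 10, each 5:5 (6.1, 7.3.3); independent-samples t-test or Mann-Whitney U at 0.05 (8.1), taken as two-sided because 8.1 does not say.

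**Assumptions.** Within-block SD of 1; a shift δ between blocks, common to both arms, of 0 to 1.5 SD; a true arm effect of 1.325 SD, which is the effect that a t-test with 10 per arm detects with 80% power when δ = 0. The plan gives no effect size, SD or power, so there is no stated figure to reproduce.

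**1. Bias with intact blocks.** Each arm has 5 of its 10 subjects in the second block, so δ adds (5/10)δ to both arm means. The difference is 0.5δ − 0.5δ = 0.

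**2. Residual SD of the unblocked test.** Within an arm, the shift puts each subject δ/2 from the arm mean. This adds 20 × δ²/4 to the residual sum of squares, which is divided by 18 degrees of freedom. The SD factor is √[1 + (δ²/4)(20/18)]:

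- δ = 0.5: √1.069 = 1.03
- δ = 1: √1.278 = 1.13
- δ = 1.5: √1.625 = 1.27

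The true standard error of the difference stays at √(2/10) = 0.447 SD, so the reported standard error is too large by these factors.

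**3. Effect on the tests.** Simulation of 100,000 trials per scenario with all 20 subjects analysed; each cell gives type I error / power:

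| Shift (SD) | t-test, no block | Mann-Whitney, no block | Linear model, arm + block |
|---|---|---|---|
| 0 | 4.9% / 80% | 4.2% / 76% | 4.9% / 80% |
| 0.5 | 4.3% / 78% | 3.7% / 73% | 4.9% / 80% |
| 1 | 2.9% / 72% | 2.4% / 66% | 5.0% / 80% |
| 1.5 | 1.5% / 62% | 1.2% / 54% | 5.1% / 80% |

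The simulated bias was within 0.002 SD in every row.

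**4. Discards and replacements.** Suppose two subjects of one arm are lost from the first block. That arm keeps 3 early and 5 late subjects; the other has 5 and 5. The bias is δ times the difference between the arms in the share of late subjects:

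- no replacement: 5/8 − 5/10 = 0.125
- both replacements in the depleted arm: 7/10 − 5/10 = 0.20
- one replacement in each arm: 6/9 − 6/11 = 0.12
- both replacements in the other arm: 5/8 − 7/12 = 0.04

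With 10% or 20% random dropout unrelated to arm, and no replacement, the average bias was within 0.003 SD.

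**5. Cost of the block term when there is no shift.** The critical value moves from 2.101 (18 df) to 2.110 (17 df), a confidence interval 0.4% wider. Power goes from 80.0% to 79.7%. In the dropout runs it goes from 74.7% to 74.0% (10% lost) and from 68.2% to 67.1% (20% lost).

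**The case against.** The strongest reply is that the planned test errs on the safe side and that the evidence for a large shift is thin. Most of this stands.

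- **A reader might infer that the unblocked comparison is biased.** The documents do not support this for the design as written, because the 1:1 ratio within each block cancels a common shift.
- **A reader might infer more false positives.** The direction is the opposite: type I error falls below 5%.
- **The 0.20 × δ figure is a worst case.** If two of 20 subjects are lost at random, the chance that both come from one arm of the first block is 20/190 = 10.5%. If replacement codes are roughly 1:1, the chance that both replacements also fall in that arm is about 10.5% × 1/4 = 2.6%. At δ = 0.5 the bias would then be 0.10 SD, against a standard error of 0.447 SD.
- **A reader might take the absence of training as evidence of a learning curve.** Section 10.9 gives existing familiarity as the reason for it, which points the other way. Section 1.1 describes clinical use in general, not at this site. The ball-tip fiber is used in both arms (1.2). The interim look comes after at least 10 operations, so it need not fall between the blocks, and 8.2 attaches no change in conduct to it. Enrollment is short and at one site.
- **Learning confined to the dusting arm would be an arm-by-block interaction.** The additive model and the simulation do not cover that.

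None of this gives a reason to leave block out of the analysis. A shift is possible, its size is unknown, and the adjustment costs almost nothing.

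**Conclusion.** The analysis does not match the randomization, and the consequence is lost efficiency. The loss depends on a shift that the documents do not quantify: about 2 points of power at 0.5 SD, 8 at 1 SD and 18 at 1.5 SD, for an assumed effect of 1.325 SD and a shift common to both arms. For a single site enrolling over 8-10 weeks, the lower end may be the more realistic, but that is a judgement. Bias is a secondary matter. It requires completers to be unbalanced across blocks, is 0.04 to 0.20 times the shift in the two-loss example with replacement, and is zero on average when dropout is unrelated to arm. The point is minor but worth settling before analysis.

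**What to change.** In 8.1, state that the arm comparisons use randomization group as a two-level factor: subjects 1-10, and all later subjects including replacements.

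- **Procedure time:** a linear model with arm and group, on the log scale if the times are skewed.
- **Catheterization time and time to discharge:** a rank test stratified by group (van Elteren), or a permutation test within group. With 20 completers at 5:5 in each group, the exact reference set has 252 × 252 = 63,504 allocations. If subjects are discarded or replaced, it must be recounted to match the allocation actually used.

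Replacement codes should not form a third level. One or two replacements might all be in one arm, and that level would then use a degree of freedom and say nothing about the difference.

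The change is one or two sentences in 8.1 and needs no new data, since the group is known from the randomization list. It costs one degree of freedom. If there is no shift, that is about 0.3 points of power with all 20 subjects analysed, and about 1 point if a fifth are lost without replacement.

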### 4 Study Objectives

#### 4.1 Primary

Demonstrate the efficiency of stone dusting Vs stone breaking of the P120H holmium laser and 200 DFL ball tip fibers

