#### 4.2 Secondary

Demonstrate the usability and safety of stone dusting

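### Section 8.1 plans between-group comparison for continuous variables only and no confidence intervals, so primary stone clearance gets no between-arm estimate and safety cannot be demonstrated from a listing

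*Combined protocol and SAP*

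**What the plan says.** Section 8.1 holds nearly the whole analysis plan. It states that "treatment evaluations and follow-up assessments will be summarized and descriptive analysis will be performed". The only between-group comparison follows: "Continuous variables will be compared between the two groups", by t-test or Mann-Whitney U test, with the rule "A p-value < 0.05 will be considered as significant". Adverse events are to be listed and graded by the modified Clavien system. Section 8.2 says that safety and the endpoints will be analysed after follow-up, but names no method.

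Section 5.1 has five primary endpoints. Three are times. The other two are "Usage of alternative stone extracting devices" and "Stone clearance based on 1 month follow-up imaging data". Section 7.2.1.5 treats clearance as a status to be confirmed by imaging. Section 7.6.3 says that the use of accessories will be recorded, and defines no count or duration.

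The objectives are worded as proof: "Demonstrate the efficiency of stone dusting Vs stone breaking" in section 4.1 and "Demonstrate the usability and safety of stone dusting" in section 4.2.

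**The concern.** The rationale in section 1.2 is that dusting shortens the procedure because small fragments wash out without extra extraction. Clearance and device use are the endpoints that check this. They are also the ones left without an inferential method. A time gain can earn a p-value, while a loss of clearance would appear only as two counts side by side, with no difference and no measure of its uncertainty.

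Safety has a similar problem. A listing with few or no complications in about ten dusting subjects may look reassuring, yet it is compatible with complication rates that matter. The objective in section 4.2 asks for more than a listing can give.

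**Working it through.** **1. Match endpoints to methods.** Procedure time, catheterization time and time to discharge are continuous, so the section 8.1 tests cover them. Clearance is a status, so it is not covered. Device use is not covered if it is yes/no, which is the natural reading of section 7.6.3 but is not stated. At least one of five, and on that reading two of five, primary endpoints have no named comparison. None of the five has a planned interval.

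**2. Arm size.** Section 6.1 gives 20 subjects and section 7.3.3 gives 1:1 allocation in each group of ten, so 20/2 = 10 per arm. The documents give no power, effect size or event rate, so there is no sample-size figure to reproduce. All counts and rates below are assumptions for illustration.

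**3. What an interval would show for clearance.** Take 9/10 in each arm. The Wilson 95% interval for 9/10 is 0.596 to 0.982. The Newcombe limits for the difference are 0 ± √[(0.900 − 0.596)² + (0.982 − 0.900)²] = 0 ± 0.315, or about -32 to +32 points. For 9/10 against 7/10 the interval is -16 to +51 points.

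**4. What zero complications would show.** With 0/10, the exact two-sided 95% upper limit is 1 − 0.025^(1/10) = 0.308, or 31%. If the true rate were 10%, the chance of seeing no event in ten subjects would be 0.9^10 = 0.35.

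**5. Which exact test.** The results below are from full enumeration of 10 against 10, two-sided. Boschloo's test orders the tables by the two-sided Fisher p-value.

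| Quantity | Fisher | Boschloo |
|---|---|---|
| p for 10/10 vs 5/10 | 0.033 | 0.013 |
| p for 10/10 vs 6/10 | 0.087 | 0.042 |
| Largest type I error | 1.3% | 4.2% |
| Power, 20% vs 80% | 64% | 81% |
| Power, 50% vs 90% | 30% | 47% |
| Power, 70% vs 90% | 6% | 14% |

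The Boschloo p-value depends on setup. In one common package the 10/10 vs 6/10 table gives 0.042 with arms as columns and 0.033 with arms as rows, so the convention must be fixed.

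**6. The time endpoints.** The 95% half-width for a mean difference is t(0.975, 18) × √(2/10) = 2.101 × 0.447 = 0.94 SD. The t-test has 80% power at a difference of 1.32 SD.

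**7. Multiplicity.** If the endpoints were independent, three tests at 0.05 give 1 − 0.95³ = 14.3% family-wise error, and five give 1 − 0.95⁵ = 22.6%.

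**The case against.** The strongest reply is that this is a small single-center study for which description is reasonable, and that anyone can compute an interval from counts in ten subjects per arm. That limits the harm but does not remove it. If the study is descriptive, intervals are the right tool and the objectives should not promise proof.

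Four stronger readings are tempting, and the documents do not support them:

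- *The yes/no endpoints are not analysed at all.* They would be summarised by arm. What is missing is a formal comparison and an estimate with its uncertainty.
- *Efficiency cannot be supported.* The three time endpoints have a test, so a very large difference, of the order of 1.3 SD, could be shown on one of them.
- *The sponsor plans to claim equal clearance.* No equivalence or non-inferiority claim is planned. That misreading is a risk to guard against, not something the documents state.
- *The plan uses a weak test.* It names no test for yes/no data. Fisher's test would also close the gap. The preference for Boschloo's test is an improvement in power, and at assumed clearance rates of 70% and 90% neither test is useful.

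Two further cautions stand. Treating device use as yes/no is an inference; if uses were counted, section 8.1 might cover it. Also, 10 per arm is not guaranteed, because section 6.1 drops subjects without the one-month visit and section 7.3.3 does not match replacements to the arm of the subject replaced.

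**Conclusion.** The concern holds in limited form. Section 8.1 confines between-group comparison to continuous variables and plans no intervals. Stone clearance certainly, and device use if yes/no, have no between-arm inference. A significant time gain could therefore be reported with no estimate of what it costs in clearance. Safety cannot be demonstrated by a listing in about ten dusting subjects, since even a clean one leaves rates up to 31% compatible with the data. Identical observed clearance of 9/10 would leave differences of about 32 points either way open.

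These figures rest on 10 evaluable subjects per arm, two-sided 95% intervals and assumed counts. Fewer subjects would widen them. The efficiency objective is not beyond reach for the time endpoints, but the plan has no rule for weighing a time gain against clearance. Adding a test alone would not cure the small sample, so the intervals matter most. The change should be made before data are seen.

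**What to change.** In section 8.1:

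- Report a between-arm estimate with a 95% interval for all five primary endpoints: a mean or median difference for times, and a risk difference with a Newcombe interval for yes/no endpoints.
- Prespecify one exact test for yes/no endpoints, preferably Boschloo's with tables ordered by the two-sided Fisher p-value, and state the convention in full.
- State which of the accessories in section 7.6.3 (baskets, forceps, saline flushing) count as device use.
- Interpret clearance from its interval, and say that a non-significant p-value will not be described as equal clearance.
- Give complication rates per arm with exact 95% intervals, beside the listing.

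In the objectives, replace the opening verb with Estimate or Compare in section 4.1, and with Describe or Estimate in section 4.2.

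The cost is a few sentences and minor programming, with no extra subjects, visits or data. The objectives will read less favourably. There will also be two more p-values among five primary endpoints, which should be labelled exploratory and stated to be unadjusted for multiplicity.
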